2. STUDY OBJECTIVES

Objectives

1. The primary aim is to assess the outcome of patients undergoing left atrial appendage ligation or closure with the SentreHeart Lariat® device as a stand-alone procedure at the participating centers
2. Secondary aims include assessment of adverse events and successful LAA closure rates

Hypothesis

Closure of the left atrial appendage with the SentreHeart Lariat® is reasonable alternative to reduce the risk of stroke in patients with an elevated bleeding risk with the use of any OAC and in whom this risk is prohibitive.

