3. STUDY DESIGN

The study is a multi-center, prospective outcomes registry. The study cohort will comprise all consecutive patients who undergo lone left atrial appendage closure using the SentreHeart Lariat® at the investigational centers and should consist of up to 50 patients. Patients will undergo follow-up visits at 7 days, 90 days, and 180 days post procedure.

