10. WITHDRAWAL

A subject may voluntarily withdraw at any time.

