11. END OF STUDY

Enrollment in this study will be completed once a subject completes all of the protocol required 90 day assessments. If a subject is unable to complete these assessments, their enrollment will be completed at the end of the 90 day window unless an appointment has been made to complete an out of window visit for extenuating circumstances. Any patients that have a failed attempt at left atrial appendage closure with SentreHeart Lariat® will be tracked through their index hospitalization for safety; their study follow up will be complete at the time of discharge.

If unsuccessful attempts have been documented to contact and arrange an end of study follow-up visit (90 day), the social security death index will be queried at a later date to confirm the subjects' status at the time of study completion.

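### For subjects who cannot be reached at the end of the study, Section 11 provides only a death-index query, so a non-fatal stroke or bleed after the last attended visit would not be found

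*Combined protocol and SAP*

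**What the plan says.** Section 3 describes a prospective registry that "should consist of up to 50 patients", and states: "Patients will undergo follow-up visits at 7 days, 90 days, and 180 days post procedure". The matrix in Section 6 places adverse event assessment at the procedure and at those three visits, and nowhere else. Section 2 leaves the outcome in the primary aim undefined, makes adverse events a secondary aim, and hypothesises that closure is a "reasonable alternative to reduce the risk of stroke" in patients for whom the bleeding risk of OAC is prohibitive. Section 12.1 lists stroke and bleeding among the known risks and says that adverse events will be adjudicated.

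Section 11 covers two situations at the final visit, which it places at 90 days:

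- **Assessments not completed:** "their enrollment will be completed at the end of the 90 day window unless an appointment has been made" for an out-of-window visit.
- **Contact attempts documented as unsuccessful:** "the social security death index will be queried at a later date", to establish the subject's status when the study was completed.

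The reviewed text contains no record review, no contact with a relative or treating physician, and no assessment by telephone. Section 15 plans descriptive summaries and a closure percentage, with no rule for missing outcomes or denominators.

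**The concern.** The fallback answers a different question from the one the registry asks. A death index returns vital status. The hypothesis is about stroke, and the population was selected for stroke and bleeding risk: Section 4.1 requires a HAS-BLED score of at least 3 and a CHADS₂-VASC score of at least 3, or 2 with justification. Most of what needs to be known about a subject who drops out of contact is non-fatal, and adverse events are collected only at visits, so anything after the last attended visit has no planned route into the data.

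The subject who is reached but cannot come in has a related gap. Section 11 offers a late visit or closure, and does not say that the contact should be used to ask about events.

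There is no comparator arm to share the under-ascertainment, and with at most 50 subjects each unknown is worth at least 2 percentage points. Some of those not seen may have missed the visit because of an event.

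**Working it through.** The plan gives no figure to reproduce: the sample size comes without a target rate, precision or loss allowance. The check is therefore of the text, followed by an illustration under stated assumptions.

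**Text, side by side**

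| Situation at the final visit | What Section 11 provides | What it can show |
|---|---|---|
| Attends, in or out of window | Visit with adverse event assessment | Stroke, bleeding, readmission, OAC use |
| Reached, cannot attend | Late visit if booked, otherwise closed | Not stated if closed |
| Not reached after documented attempts | Death-index query | Vital status only |

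The fallback is tied to the 90-day visit, whose window closes at day 90 + 15 = 105. Sections 3, 5.3.3, 6 and 7 run follow-up to 180 days, with a window opening at day 180 − 30 = 150. As written, a missed 180-day visit has no stated fallback at all.

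**Inputs for the illustration**

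- N = 50, the maximum in Section 3.
- x = observed events; m = subjects of unknown status; f = fraction lost; k = relative risk in those lost. All four are assumptions, because the documents give none of them.

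**Bounds.** The proportion with an event lies between x/N and (x + m)/N.

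| m unknown | x = 0 | x = 2 |
|---|---|---|
| 1 | 0/50 to 1/50 = 0–2% | 2/50 to 3/50 = 4–6% |
| 3 | 0/50 to 3/50 = 0–6% | 2/50 to 5/50 = 4–10% |
| 5 | 0/50 to 5/50 = 0–10% | 2/50 to 7/50 = 4–14% |
| 10 | 0/50 to 10/50 = 0–20% | 2/50 to 12/50 = 4–24% |

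The upper bound requires every unknown subject to have had an event, so it is a limit and not an estimate.

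**Differential risk.** With observed rate p = 4% among those followed, the overall rate is (1 − f)p + f·k·p.

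| f | k = 1 | k = 2 | k = 4 |
|---|---|---|---|
| 5% | 4.0% | 3.8 + 0.4 = 4.2% | 3.8 + 0.8 = 4.6% |
| 10% | 4.0% | 3.6 + 0.8 = 4.4% | 3.6 + 1.6 = 5.2% |
| 20% | 4.0% | 3.2 + 1.6 = 4.8% | 3.2 + 3.2 = 6.4% |

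**Scale.** With complete data, 2/50 has an exact 95% interval of 0.5–13.7%. With 5 subjects dropped, 2/45 = 4.4% has an interval of 0.5–15.1%. Neither interval allows for what happened to the missing subjects. The shifts in the last table are small beside these intervals, whereas the worst-case bound at m = 5 (14%) is about as far out as the upper limit for complete data.

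**The case against.** The strongest reply is that the gap is narrow. The death-index query follows only documented failed attempts at contact, out-of-window visits are allowed, and findings up to the last attended visit stay on record. If contact is made and a stroke is mentioned, Section 12.1 would have it handled as an adverse event. Stroke and bleeding are not named endpoints in what is a descriptive registry. All of this stands, and it confines the point to status after the last attended visit. It does not supply a means of learning that status for a subject who is not reached, nor does it make the enquiry a planned step for one who is reached but not seen.

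Three stronger readings are tempting, and the documents do not support them:

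- **That those lost are the subjects most likely to have had an event, so the results favour the device.** Nothing in the documents says who will be lost or at what risk. Unascertained events can only lower the count, but the effect on a rate among those followed depends on k, and at k = 1 there is none.
- **That a subject found alive in the index would be counted as free of stroke.** Section 15 has no such rule. The difficulty is that it has no rule either way.
- **That withdrawn subjects are left with nothing.** Section 10 is brief ("A subject may voluntarily withdraw at any time"), but data up to withdrawal remain, and consent terms on later use of records are not among the pages available. This is mostly missing detail.

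**Conclusion.** The point holds for subjects not reached, or reached but not seen, at the final visit, and for events after their last attended visit. For them the plan secures at most vital status, in a single-arm study whose hypothesis concerns stroke. Stroke and bleeding could be under-counted. The documents cannot say by how much, because loss, event rate and relative risk are all assumed above: moderate assumptions move 4% to roughly 4.2–6.4%, and only the extreme case, with every unknown an event, reaches the upper bounds. This is a worthwhile, inexpensive improvement in ascertainment and not a flaw that invalidates the registry.

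**What to change.** In Section 11, before closing out a subject who does not attend:

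1. Require a scripted remote contact with the subject or, if the subject is unreachable, with a relative or the treating physician, and a review of available medical records.
2. Record stroke or TIA, systemic embolism, major bleeding, readmission and OAC use, and the date last known event-free.
3. Keep the death index for vital status only.

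In Section 15, state that a subject known only to be alive is reported as *stroke status unknown* and not as event-free, and give the number of such subjects beside each event proportion.

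Reconcile the 90-day end of study in Section 11 with the 180-day follow-up in Sections 3, 5.3.3, 6 and 7, and attach the procedure to whichever visit is then final.

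The cost is a protocol amendment, a short call script, consent wording that covers relatives, physicians and records, and a few calls or record requests. No visits, procedures or patients are added. The consent wording should be settled early, since records may not be obtainable later without it.

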12. RISKS/BENEFIT

12.1 Risks and Adverse Event Reporting

The study is a multi-center, prospective outcomes registry. Adverse events will be reviewed, adjudicated and reported per IRB policy

Known risks associated with the SentreHeart Lariat® procedure:

- Pericardial Effusion
- Cardiac Tamponade
- Device Embolization
- Atrioventricular Fistula
- Cardiac Perforation
- Thrombus
- Bleeding
- Bruising/Hematoma
- Arrhythmia
- Pseudoaneurysm
- Valvular Damage
- Stroke
- Conversion to Surgery
- Death

12.2 Minimization of Risks

Patient safety during this study will be the highest priority. The patients will not incur any psychological, social, legal or economic risks by participating in this study.

12.3 Benefits

Left atrial appendage closure with the use of SentreHeart Lariat® may reduce subjects' risk of stroke. Information learned from this study may help in the management of patients with atrial fibrillation and atrial flutter who are at elevated bleeding risk with the use of any OAC therapy.

13 DATA MANAGEMENT

13.1 Data Storage:

An appropriate database will be created and managed in compliance with HIPAA regulations. Data will be stored safely in a secure environment, and maintenance for back-up purposes will be performed on a routine basis to avoid data loss.

13.2 Research Subject Privacy

Patients will be approached discretely and privately by the study coordinator. The discretion of the study coordinator will be used to judge if privacy (from both medical personnel and other persons in the hospital) is ensured during the consent process. The patient will be informed that they can stop the consent process at any time if they feel their privacy is being compromised, and no information will be collected directly from the patient after that point. Patients will be informed that participating / not participating in this study will in no way affect their care and that they are in no way obligated or expected to participate. If the patient agrees to participate, they will be taken through the informed consent process. Upon data collection/acquisition, study identifiers will be encrypted to protect patients' privacy and meet HIPAA regulations, and data will be stored in a secured database while periodic back-up. All hard copy material (summary printouts) will be stored securely and all electronic storage media will be safely stored as per HIPAA regulations. All patient identifiers will be removed from research related documents and a study specific identifier assigned to each subject. Only de-identified data will be used for analysis and only aggregate results will be reported. Only those directly related to the research will be allowed access to subject information.

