4. STUDY POPULATION

The study cohort will consist of up to 50 patients who are candidates for LAA closure in whom oral anticoagulation is contraindicated.

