5. ENROLLMENT & STUDY PROCEDURES

Subjects evaluated for left atrial appendage closure will be screened for inclusion and consented prior to their procedure. During clinical evaluation of the patient, the physician investigator will assess those items described in Table 1. If the anatomy is favorable for placement of the Lariat® device, the procedure will be performed at one of the participating centers. If anatomy is not favorable, the patient will be excluded from the study and managed using best care practices by his or her physician. Please note, at The Heart Hospital Baylor Plano, the Lariat device is only available to patients participating in the study.

Subjects consented will be tracked by the study team and will be considered enrolled in this study at the time of the start of their left atrial appendage closure procedure. All subjects that are consented who do not undergo left atrial appendage closure with SentreHeart Lariat® will be considered screen failures. Any patients that have a failed attempt at left atrial appendage closure with SentreHeart Lariat® will be tracked through their index hospitalization for safety; their study follow up will be complete at the time of discharge.

The invasive procedure for placement of the study devices will proceed according to standard interventional techniques, as already in place at the participating centers. Patients undergoing the Lariat® procedure will be administered colchicine 0.6 mg po twice daily for a minimum of three days preoperatively, and 30 days postoperatively. (This dose may be adjusted for renal function or intolerance).

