15 STATISTICAL ANALYSIS & DATA MANAGEMENT

Data on the clinical and non-clinical risk factors will be summarized using means, standard deviations (SDs) and percentages. Successful left atrial appendage closure will be reported as a percentage

Table 1. Patient screening tool

1. Atrial fibrillation or atrial flutter documented? Yes No
 Paroxysmal Short-lasting persistent Longstanding persistent

2. EP consultation to exclude candidacy for ablation? Yes No
 catheter or surgical

3. CTA obtained to assess LAA anatomy? Yes No
 If yes, was anatomy favorable for this procedure? Yes No
 If no, justification for procedure:

If no, was second opinion obtained? Yes No
 Physician rendering second opinion: _____

4. CHADS₂-VASC score _____ of 9
 a. CHF _____ of 1
 b. Hypertension _____ of 1
 c. Age >65 yrs _____ of 1
 d. Diabetes Mellitus _____ of 1
 e. Stroke or TIA _____ of 2
 f. Vascular Disease _____ of 1
 g. Age >75 _____ of 1 (in addition to age>65)
 h. Sex Category _____ of 1 (Male=0; Female =1)

5. CHADS₂ score: _____ of 6
 a. CHF _____ of 1
 b. Hypertension _____ of 1
 c. Age >75 yrs _____ of 1
 d. Diabetes Mellitus _____ of 1
 e. Stroke or TIA _____ of 2

6. HAS-BLED SCORE _____ of 9
 a. Hypertension _____ 1
 b. Abnormal renal and hepatic function ² _____ 1-2
 c. Stroke _____ 1
 d. Bleeding tendency/predisposition³ _____ 1
 e. Labile INRs on warfarin⁴ _____ 1

¹Systolic BP >160 mmHg

²Renal: serum creatinine >2.25 mg/dl
 Hepatic: Bili 2-3x normal and
 AST/ALT/ALK-P >3x normal or chronic
 disease (cirrhosis)

³History of bleeding or anemia

⁴Time in therapeutic range <60%

⁵Concomitant antiplatelet or NSAID use or
 excess alcohol

f. Elderly (>65 yr) 1
g. Drugs or alcohol (1 point each)⁵ 1-2

6. If CHADS₂-VASC score<3, or if HAS-BLED score is <3, list justification for procedure:

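### Section 13.2 promises that declining has no effect on care, but Section 5 restricts the device to study participants at one named centre

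*Combined protocol and SAP*

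**What the plan says.** Section 13.2 (Research Subject Privacy) prescribes what the study coordinator conveys on approaching a patient: that "participating / not participating in this study will in no way affect their care". The sentence applies to all centres and has no exception. The section then says that those who agree go on to the informed consent process.

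Section 5 (Enrollment & Study Procedures) describes screening and adds a note about one named participating centre, where "the Lariat device is only available to patients participating in the study". The same section fixes the order of events: "Subjects evaluated for left atrial appendage closure will be screened for inclusion and consented prior to their procedure".

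Section 8 (Screening) repeats the screening text of Section 5 but leaves out the note on restricted access.

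**The concern.** The person being approached is under evaluation for closure of the left atrial appendage. At the named centre the device used for that procedure can be had only by joining the study. Telling that person that refusal changes nothing about their care leaves out the one consequence that bears most directly on the decision.

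What is at stake is the accuracy of the information given before a decision, not a number in the results. A candidate could decline in the belief that the device remains available at that centre outside the study. The protocol itself treats the device as a possible benefit (Section 12.3: "Left atrial appendage closure with the use of SentreHeart Lariat® may reduce subjects' risk of stroke"), and the people concerned are "candidates for LAA closure in whom oral anticoagulation is contraindicated" (Section 4), so they cannot simply fall back on the usual drug treatment.

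**Working it through.** No arithmetic applies. The check sets the relevant sections side by side and looks for text that would reconcile them.

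1. **Scope of the assurance (Section 13.2).** It covers both participating and not participating, allows no degree of effect, and names no centre. It speaks of care in general and does not limit itself to standard or other care.
2. **Access to the device (Section 5).** At one named centre, access depends on participation.
3. **Order of events (Sections 5 and 13.2).** The patient is approached and given the assurance. If willing, the patient goes through consent, and the procedure follows. A refusal therefore always comes before any use of the device.
4. **Consequence at the named centre.** From 2 and 3, a candidate who declines cannot receive the device there. From 1, that candidate has been told that declining has no effect. Both statements cannot be true at that centre.
5. **Is the device part of the candidate's care?** The candidate is being evaluated for this type of procedure, oral anticoagulation is contraindicated (Sections 4 and 4.1), and Section 12.3 says the device may lower stroke risk. Section 1 also indicates that alternatives are limited: the two internal occlusion devices it describes need at least 45 days of oral anticoagulation, surgical excision is generally done alongside another cardiac procedure, and the surgical clip has no stand-alone indication. Losing access to the device at the treating centre is an effect on care.
6. **Search for qualifying text.** None was found. Section 8 omits the access note, so staff working from it alone would not see the restriction. Sections 5 and 8 say how patients with unfavourable anatomy will be managed, but give no corresponding statement for patients who decline. Sections 4.3.1 and 9 require discussion of the objective, risks and benefits, with questions answered before signing, but do not mention access.
7. **Bearing on the analysis.** Under Section 15, risk factor data "will be summarized using means, standard deviations (SDs) and percentages", and closure is reported as a percentage. No planned quantity depends on the wording in Section 13.2.

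**The case against.** The strongest reply is that Section 13.2 is a privacy section, not the consent document. The consent pages are not in the reviewed documents, and the form may state the access restriction plainly. The discussion required by Section 9 could also bring it out before anyone signs. This stands as a limit: a reader might infer that candidates actually give consent on a false statement, and the documents do not establish that. It does not remove the conflict. Section 13.2 puts the assurance ahead of formal consent, so someone who declines at the first approach may never reach the form. If the form does disclose the restriction, it disagrees with the protocol.

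A second reply is that such assurances are commonly meant to cover care that would be available anyway, and that Section 13.2 pairs this one with a statement that nobody is obliged to take part. That intention is plausible, but the sentence is absolute and does not say so.

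A third reply is that a patient who declines might obtain the device elsewhere. The documents do not say so, and care at the named centre would still differ.

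Three stronger readings are tempting, and none is supported:

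- **Different selection by centre.** The documents are silent on whether other centres offer the device outside the study; the same restriction could apply there. Section 3 sets one rule for all centres: consecutive patients undergoing the lone procedure.
- **Exposure to the procedural risks in Section 12.1.** The assurance does not understate those risks or push anyone towards the procedure. Those it may mislead are people who decline and so do not undergo the study procedure.
- **A share of the up to 50 subjects.** Under Sections 5 and 9 a subject is enrolled only when the procedure starts. Those who decline fall outside that number.

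**Conclusion.** The conflict is real and confined to the protocol's wording: at one named centre, following Section 13.2 as written gives candidates an untrue assurance. It concerns everyone approached at that centre and matters most for those who decline. The documents do not state how many that will be. No effect on any estimate is shown.

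The conclusion rests on three assumptions: that the access note in Section 5 is current, that staff say what Section 13.2 prescribes, and that care includes the procedure for which the patient is being evaluated. It does not depend on what the consent form says. The correction is worth making even though it changes no result, because it alters what candidates are told before they decide and costs very little.

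**What to change.** Reconcile the two sections. If the access note in Section 5 stands:

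- Qualify the sentence in Section 13.2 to say that refusal does not affect the patient's other care or relationship with the centre, but that where the device is offered only within the study, declining means it will not be available at that centre.
- Repeat the access restriction in Section 8, so that the two screening descriptions match.
- Check that the consent form and the consent discussion at the named centre say the same.

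This needs IRB review of a short text change. It requires no additional patients, data or analysis. The small downside is that the revised statement reassures less than the present one.

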14 DATA MONITORING

Internal monitoring will be conducted periodically and reviewed by the data monitoring committee. CRFs, source documents, informed consent forms, and study deviations will be included; these findings will be reported to the PI. Deviations will be documented and reported according to IRB policy.

Regulatory documents will be audited by the Baylor Research Institute Department of Research Compliance upon request.

